7. METHODS OF DATA COLLECTION

Work package 1 – Systems mapping and perspectives

This WP will be in three stages. In stage 1, a draft actor map will be produced based on the existing literature on determinants and enablers of PA based on the work of Rutter (2019). This draft map will be presented to stakeholders at a half day workshop in which it can be amended to reflect any specific characteristics of the local context. System intervention entry points including primary care, education, transport and infrastructure, leisure and recreation, workplaces will then be mapped using the local knowledge of stakeholders.

In stage two, a conceptual map will then be produced of the local system for PA showing the relationships between the different components. The map will be fed back to stakeholders for further comment in a second workshop at which a graphic recorder will record the relationships and feedbacks suggested by participants.

The third stage will comprise online/telephone interviews with stakeholders who currently act or could act as referrers to the HWBS to gather their views and perspectives on their part in the system: their awareness and understanding of the scheme, their awareness and understanding of PA for health conditions, their access to digital platforms for service users, their relationship with others in the scheme. At this stage, the stakeholder representatives will be given the opportunity to provide feedback on the actor map for its final refinement.

Work package 2 – Service evaluation from referral perspective

We will aim for all groups to participate in three interviews to facilitate case to case comparison and demonstration of change over time. However, a pragmatic approach will be employed if required, with consideration to timepoint of recruitment and levels of engagement with the evaluation e.g., referrals choosing to not attend the service may only be able/willing to participate in one or two interviews.

Participants will be invited to three interviews over the course of six months (i.e., around month 1, 3.5 & 6). Interviews will be transcribed verbatim by a University approved service. The semi-structured topic guide will be devised by the research team, in

collaboration with the partner and PPIE representatives to explore, for example, perceptions of specific characteristics of the service (such as cost, length, referral routes and the personalised programme), facilitators and barriers to use of the service, attitudes towards PA, effects on lifestyle and intentions for engagement with the service and PA in the future. Questions will be designed to be open-ended to ensure that researchers do not impose their views on the narrative.

It should be noted that Interpretive Phenomenological Analysis (IPA; Smith et al., 2009; see data analysis section) typically endorses deep level analysis of one dimension within one group and at beginner level this may involve recruiting between three and six participants. Making case to case comparisons and longitudinal study requires a larger sample (Hefferon & Gil-Rodriguez, 2014). Accordingly, the work package will be conducted by three researchers, overseen by a researcher with post-doctoral level experience in conducting and teaching advanced qualitative methods.

Quantitative data, to supplement the qualitative interviews, will be transferred by the local authority partner to the research team, this will be cleaned as required ahead of statistical analysis.

Work package 3 – Service evaluation from targeted non-users' perspective

Survey data will be collected from the eligible participants by trained researchers, following a questionnaire loaded into the Qualtrics offline surveys app for mobile phones. The researchers will read each question as written to participants and record responses directly into the app. At the end of each completed survey, data is either stored securely in the app or (if wi-fi is available or data roaming enabled) transferred to the central password protected database. The app allows visual stimuli to be shown if prompted awareness questions are required. Quality control metrics including geo-location, time and date stamps for each completed questionnaire are incorporated into the system.

Work package 4 – Cost analysis

The cost analysis work package will be undertaken in a collaborative way with the service providers in the following stages:

- Workshop 1: Exploring unit costs associated with delivering BFHWBPAS, identifying which data is already held and which will need to be collected.
- Local stakeholders begin retrieving data
- Workshop 2: Building cost picture, identifying data limitations.
- Local stakeholders continue data retrieval
- Workshop 3: Final review of unit cost data
- PHIST South Bank undertake analysis and report writing.

The local stakeholders will collect associated unit cost data with support from PHIRST South Bank. The exact nature of these costs will be identified through the workshopping process but are likely to include staff time (i.e. all staff involved, their hourly rates and total number of hours involved in the project), the total budget allocated to the programme and the cost of the actual intervention (disaggregated and described separately to the overall budgetary costs), any additional training costs, any additional building rental, office space or equipment cost as well as additional IT and travel costs.

8. DATA ANALYSIS

Work package 1 – Systems mapping a

The initial and follow up workshops will produce a conceptual 'map' of the multiple factors that constitute the system and the cross-sectoral nature of the influences on physical activity illustrating the breadth of opportunities to influence the system. The initial map will be based on existing literature and the work of Rutter et al, (2019). Qualitative systems mapping will be used to develop the map based on feedback from the core working team and wider stakeholder groups which will be captured via graphic recording and through the process of facilitation. Interviews will be analysed using Framework Analysis.

Work package 2 – Service evaluation from referral perspective

With a view to addressing the question, "how do referrals think about the service in terms of affect, acceptability and perceived impact?", IPA will be used to explore referrals' experiences and perceptions. Data will be stored and coded using the qualitative software NVivo. No prior assumptions about the data will be made. The qualitative methodology will capture idiographic experience of service involvement, allow cross-case analysis and illustrate processes of change. It may be supplemented by descriptive statistics from the partner survey capturing reasons for service discontinuation.

For the quantitative component, data collected by the partner will be descriptively analysed e.g., service uptake by deprivation level, age, ethnicity, health status. Population data will be statistically analysed for changes in health indices e.g., blood pressure, body mass index, mental wellbeing, personal wellbeing. Health indices at baseline will be compared to those at 12 weeks, and stratified according to different individual characteristics e.g., health status at baseline, activity level at baseline, programme adherence. Descriptive and statistical analysis will be accomplished using Microsoft Excel and SPSS Statistics software packages.

Work package 3 – *Service evaluation from targeted non-users' perspective*

The final dataset will be downloaded from the Qualtrics database into the *SPSS Statistics* software package, cleaned and analysed for main patterns and associations in the distributions of its categorical variables. Responses to open-ended questions will be recoded for quantitative analysis. There are no pre-existing hypotheses; the aim is to develop insight from the data itself, which, when aligned with prior knowledge, will lead to actionable recommendations.

Work package 4 – Cost analysis

A descriptive analysis of costs will be undertaken with a distinction between commissioned cots and actual costs. A breakdown of income generated will also be captured. Data will be analysed alongside service user patient monitoring data collected as part of work package 2 and where data allows basic cost impact assessments made. Where data quality permits the analysis team will also work with BF colleagues to explore the combination of;

- a) Resource use collected
- b) Unit cost data associated with the above

c) Any suitable and/or appropriate outcome data (such as Quality of Life, Life Expectancy or change in diastolic and/or systolic blood pressure) – where quality and completeness criteria are met.

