To differentiate from ERS, such interventions have been termed '*PA referral schemes*' (Hanson et al., 2020) and encompass all schemes that (1) have the primary aim of increasing PA; (2) have a formalised referral process; and (3) are provided for individuals who are inactive/sedentary, and/or have or are at risk of a health condition. Specific examples include entry routes via self-referral or from other professionals (e.g., health trainers) and group-based needs assessments (Hanson et al., 2020). Both self-referred and NHS-referred individuals have benefited from sport-led community programmes (Garner-Purkis et al., 2020). The value of such schemes appears promising, however, unlike the traditional ERS model, the effectiveness of these newly formatted PA referral schemes for reducing inactivity has not been evaluated. Elements that are effective for engaging some populations with exercise may be less effective for other populations, especially for different age groups (Craike et al., 2018). Understanding which elements of the PA referral scheme is important for developing strategies for the management and prevention of chronic health conditions.

The whole-system approach to increasing PA

In evaluating the effectiveness of PA interventions, the wider landscape and multiple levels of influence on health-related behaviour e.g., social and environmental factors (Speake et al., 2016) should be considered (Hull et al., 2018; Hull et al., 2021). The five quality statements set by NICE (2019) for encouraging PA in the community involves embedding senior level PA champions within local authorities and healthcare commissioning groups; prioritisation of sustainable active travel; community member co-design and management of public open spaces; workplace and school programmes. Achieving these objectives requires working with a range of partners (for example, the voluntary sector, community groups, faith groups, education sector, businesses, and disability groups) and ensuring that the setting of priorities is jointly agreed. Co-production between communities, user groups and deliverers in the development of PA interventions is recommended (Copeland et al., 2012).

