3. THEORETICAL FRAMEWORK

The coproduction workshops attended by the evaluation team, local stakeholders and PPIE representatives resulted in the development of a logic model of the BFHWBPAS project evaluation (see Figure 1) underpinned by *The Theory of Change*. The model assumes that the design of the scheme will increase its acceptability and accessibility and improve service users' health outcomes and establish a sustainable and coherent system partnership.

This model encompasses a series of *'if...then...'* statements and assumptions (see Downey & Golder, 2022):

- a) If service users are given a 1-1 appointment with a coach during which a co-created plan is created, then there is a greater chance of a sustained change in PA because the service is tailored to them, so, they are more likely to commit.
- b) If service users can choose from a variety of forms of exercise and are offered flexibility, including the option for social interaction, then adherence will improve because they have more personal choice and enjoyment.
- c) If service users in deprived areas are directly offered the scheme, then they are more likely to participate because it has no cost and there will be fewer barriers to access
- d) If all referrers (primary care, social prescribing and voluntary sector) have a clear understanding of the nature and aims of the scheme, have some training, have clear, accessible guidance and there are processes to support referral, then they will participate more and refer more appropriately.
- e) If all practitioners involved with a potential service user have a clear understanding of the scheme and other partners continuity will improve and people referred will be suitable, and inter-professional/inter-sectoral cooperation and mutual value will improve.

The logic model guided the design of the three work packages.

Figure 1: Logic model for evaluation of the HWBS intervention

4. **RESEARCH QUESTION/AIM(S)**

4.1 Aim:

The aim is to evaluate the new Health and Wellbeing Physical Activity Service in Bracknell Forest and the relationships and structures that support the delivery of this intervention.

4.2 Questions:

- What is the level and process of engagement of agencies and structures in the local health and social care system with the BFHWBPAS?
- How do the specific characteristics of the BFHWBPAS (e.g., cost, length, referral routes, personalised program) influence uptake, engagement, acceptability and impact on users and target populations?

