
4.3 Objectives Aligned to Work Packages (WP)

- To identify the elements of the health and social care system that have the potential to support and promote engagement in PA via exercise referrals. (WP1)
- To explore the views, experiences, interactions and perceived impact of agents across the health and social care system of the HWS and establish the implications for uptake, engagement, impact and delivery. (WP1)
- To explore the experience, acceptability and health impact on different categories of participants in the BFHWBPAS- referred and attended; referred and did not attend; referred, attended and subsequently dropped out. (WP2)
- To understand the factors that act as perceived barriers and enablers to uptake in the BFHWBPAS amongst members of the target groups from the socially disadvantaged areas not currently accessing the service. (WP3)
- To identify the cost of delivering the service (WP4)

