Purposive sampling will be used for the qualitative data component. The researchers will aim to recruit 20 participants who are 18 years of age or over, have provided consent for data to be shared with the evaluation team and have been recently referred to the service. We will follow the journey of those who are i) referred and will go on to attend the service ii) referred but will not go on to attend the service and iii) referred, do attend but later drop out. This sample size could result in up to 60 interviews in total across three time points. The literature indicates that attrition for ERS may be up to fifty percent, in which case, around 10 participants from the proposed sample would be expected to fall into group one, perhaps less when also accounting for evaluation attrition. Written or recorded verbal consent will be sought prior to participants continuing to attend the service, we will actively recruit individuals referred to the service who do not become service users.

For the quantitative data component, all enrolled participants will be included in the sample population following informed written consent which will be sought during the enrolment process by the partner. The sample population will be stratified in accordance with demographics and characteristics such as health status, ethnicity, and age. There will likely be two referral pathways, one for GPs using existing referral systems and one on the 'JOY' Application which will be used by the social prescribers and the voluntary sector. The partner has submitted a request for a permissions box to be added to both to enable details of potential participants to be shared with the evaluation team. If appropriate, the partner gatekeeper managing this system will then securely transfer this data to the appropriate researcher(s) in line with the data sharing agreement.

To compensate participants for their time, we will explore the use of a voucher incentive (approximately £15 for each 30-minute interview, £25 an hour). The proposed voucher value will be discussed amongst our PPIE representatives and the evaluation team to confirm that this is perceived as reasonable.

Work package 3 – Service evaluation from targeted non-users' perspective

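### WP2 states health impact only as a before-after comparison within strata, which cannot show whether impact differs between groups of users

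*Protocol*

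**What the plan says.** Section 8 (work package 2) first plans a descriptive account of uptake by deprivation, age, ethnicity and health status. It then turns to inference: "Population data will be statistically analysed for changes in health indices", with the examples "blood pressure, body mass index, mental wellbeing, personal wellbeing". The comparison is specified in one sentence: "Health indices at baseline will be compared to those at 12 weeks, and stratified according to different individual characteristics". The example characteristics are "health status at baseline, activity level at baseline, programme adherence".

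Section 6 (work package 2) adds: "The sample population will be stratified in accordance with demographics and characteristics such as health status, ethnicity, and age". It includes all consenting enrolled participants and gives neither a total nor stratum sizes. The risk register in section 9.2 mentions a required sample size and power for these data, without a figure.

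The questions that this analysis could serve are in section 4. The second research question in 4.2 asks how features of the service "influence uptake, engagement, acceptability and impact on users and target populations". The WP2 objective in 4.3 is "To explore the experience, acceptability and health impact on different categories of participants in the BFHWBPAS", meaning those who attended, did not attend or dropped out.

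No comparison of change between strata, and no interaction term, appears anywhere in the protocol.

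**The concern.** The stated comparison and the stated question have different null hypotheses. A before-after comparison inside a stratum addresses whether the mean change there is zero. A question about impact on different kinds of user needs to know whether the mean change is the same in each.

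A table of stratified before-after results invites the reader to supply the missing contrast by eye: significant here, not significant there, so the service works for one group and not the other. Whether a stratum reaches significance depends on its size as well as on its change, so a small group can appear not to benefit simply because it is small. Section 4.4 promises recommendations for improving the service and guidance for other councils, and section 2 gives reducing inequalities in physical activity as a purpose. A false statement that some group does not benefit would therefore have practical consequences.

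**Working it through.** **Plan's own figure.** There is none to reproduce. The protocol gives no WP2 sample size, significance level, effect size or standard deviation (SD). The figure of 366 in section 6 belongs to WP3.

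**Assumptions for illustration.** Two independent strata of sizes n1 and n2; the same true mean change d in both, in units of the SD of change; normal data; complete follow-up; two-sided 5% paired t-tests. All sizes and effects are assumed.

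**Formulas.** Power p in a stratum of size n comes from the noncentral t distribution with n − 1 degrees of freedom and noncentrality d√n. The chance that exactly one of two strata is significant is p1(1 − p2) + p2(1 − p1).

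| d | n1 / n2 | p1 | p2 | Exactly one significant |
|---|---|---|---|---|
| 0.3 | 180 / 20 | 0.980 | 0.247 | 74% |
| 0.3 | 100 / 25 | 0.844 | 0.302 | 64% |
| 0.3 | 160 / 40 | 0.965 | 0.457 | 54% |
| 0.2 | 100 / 100 | 0.508 | 0.508 | 50% |
| 0.3 | 240 / 60 | 0.996 | 0.628 | 37% |
| 0.3 | 100 / 100 | 0.844 | 0.844 | 26% |
| 0.5 | 160 / 40 | 1.000 | 0.869 | 13% |
| 0.5 | 240 / 60 | 1.000 | 0.968 | 3% |
| 0.3 | 200 / 200 | 0.988 | 0.988 | 2% |
| 0.5 | 100 / 100 | 0.9986 | 0.9986 | 0.3% |

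Worked row (0.3 SD, 160/40): 0.965 × 0.543 + 0.457 × 0.035 = 0.524 + 0.016 = 0.540.

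**Direct test.** A two-sample t-test of the change scores, with equal true change, rejected in 4.8% to 5.1% of 20,000 simulated studies for strata of 50/50, 100/25, 100/100 and 150/50.

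**Error in the other direction.** With true changes of 0.3 and 0.6 SD and 100 per stratum, the two powers are 0.844 and 1.000. Both strata are significant in 0.844 × 1.000 = 84% of studies, so a twofold difference goes unremarked.

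**Which direct estimate.** One might regress the 12-week value on the baseline value and the group (ANCOVA). The groups here are not randomised and may differ at baseline. With equal true change, equal SDs at both times, a baseline-to-12-week correlation of 0.7 and a baseline gap of 0.5 SD, the ANCOVA group coefficient is expected to be 0.5 × (1 − 0.7) = 0.15 SD, not zero. In simulations of 5,000 studies it was significant in about 20% of runs (160/40) to 30% (100/100), while the difference in change scores stayed near 5%. ANCOVA answers a different question: whether people with the same baseline value end differently.

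**The case against.** The strongest reply is that the protocol does not plan the mistake. It names no test per stratum, no significance level and no rule for declaring groups different. A stratified comparison could mean estimates by subgroup, or a model with a stratum-by-time term. The exact method is commonly left to an analysis plan, which is not among the documents reviewed. This stands. A reader might infer that WP2 will repeat a significance test in each stratum and report groups as unequal on that basis; the text does not support that.

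A reader might also infer that the sentence on change is aimed at ethnic minorities or deprived groups. It is not so specific. Its examples are baseline health status, baseline activity and adherence. Ethnicity and age come from section 6, and in section 8 they belong to the uptake description. Both lists are examples, so such strata remain possible but are not fixed. Section 1.3 gives limited support, since "Elements that are effective for engaging some populations with exercise may be less effective for other populations" concerns engagement rather than change in health.

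Finally, section 5 gives the use of the service data as judging whether impact matches other exercise referral schemes, which is an overall question, and section 7 calls these data a supplement to the interviews. The categories in section 4.3 are attendance groups, which only the adherence stratum partly matches. This limits the weight of the point. It does not remove it, because 4.2 and 4.3 still ask about impact on particular groups and the one comparison stated cannot answer that. An analysis plan that merely carried out the sentence would keep the mismatch.

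**Conclusion.** The point holds in a limited form. The only inferential comparison stated for WP2 health impact is baseline against 12 weeks, broken down by individual characteristics. It can show whether each stratum changed, and it cannot show whether strata changed differently.

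The consequence is conditional. If strata are contrasted by their significance, equal benefit can look unequal. In the cases tabulated this happens in 0.3% to 74% of studies, against about 5% for a direct test. The high rates need small or unequal strata and modest change; with large strata or large effects the problem nearly vanishes. Since the protocol fixes neither sizes nor effects, a claim that this will often happen, or any single multiple of 5%, is not supported. The calculation assumes complete data and normal changes.

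**What to change.** Add two or three sentences to section 8, work package 2:

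- Any conclusion about differential impact will rest on a direct estimate of the between-stratum difference in mean change (12 weeks minus baseline) with its 95% CI.
- Mean changes within strata will be shown with CIs as description only.
- No group will be called a non-beneficiary because its own before-after comparison is non-significant.

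If an ANCOVA is also reported, its group coefficient should not be presented as the difference in change. Where a stratum is defined by the baseline value of the outcome itself, the report should note that regression to the mean affects the comparison of changes.

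This needs no new data and runs in SPSS, which the protocol already names. The cost is precision. With strata of 160 and 40 and equal SDs of change, the half-width of the 95% CI is 1.97 × √(1/160 + 1/40) = 1.97 × 0.177 = 0.35 SD of change, so fewer subgroup statements will be possible.

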5. STUDY DESIGN AND SETTING

To address the complexity of the four **research** objectives, this evaluation will adopt a mixed-methods research design and comprise of three work packages operating sequentially with overlapping phases.

Work package 1 – Systems mapping

Through Actor mapping, the initial phase of this evaluation will identify the key organisations, individuals and factors influencing PA in the local area, operating across multiple levels in accordance with the Whole Systems Mapping Approach (PHE 2019 and 2021). This map will be used to explore the existing PA system and how and where this service sits within the local system. There will be an initial mapping workshop with stakeholders involved with funding, promoting and referring service users with a follow up workshop after two months. Online/Telephone interviews with the identified key stakeholders representing various roles e.g., policy makers, practitioners, service delivery managers across multiple levels of the service delivery will explore their experiences of the service design, implementation, and referral pathways. They will also review the Actor map and offer feedback for its refinement. The workshops, COVID-19 guidance permitting, will take place onsite at a location of the partner's choosing.

Work package 2 – Service evaluation from referral perspective

This work will follow a prospective approach comprising longitudinal qualitative case study interviews with BFHWBPAS participants supplemented by Everyone Active's survey data (recording reasons for service discontinuation) and a statistical analysis of service data (routine outcome data collected by the partner). The latter will allow an understanding of whether the BFHWBPAS achieves an impact in line with other researched ERS. Interviews will take place via Microsoft Teams audio/video call or telephone call, depending on participant access and preference.

Work package 3 – Service evaluation from targeted non-users' perspective

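### Work package 2 is meant to judge the service's impact from an uncontrolled baseline-to-12-week change, which cannot support that inference

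*Protocol*

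**What the plan says.** Section 8 (work package 2) defines the quantitative outcome analysis. The outcomes are given by example: "Population data will be statistically analysed for changes in health indices e.g., blood pressure, body mass index, mental wellbeing, personal wellbeing". The comparison is within person: "Health indices at baseline will be compared to those at 12 weeks, and stratified according to different individual characteristics e.g., health status at baseline". The full list of example strata is "health status at baseline, activity level at baseline, programme adherence".

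Section 6 fixes who is analysed: "For the quantitative data component, all enrolled participants will be included in the sample population following informed written consent". No comparison group or external series is planned.

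Section 5 fixes the inference to be drawn from this statistical analysis of routine data: "The latter will allow an understanding of whether the BFHWBPAS achieves an impact in line with other researched ERS". Section 4.3 makes health impact part of the objective for this work package: "To explore the experience, acceptability and health impact on different categories of participants in the BFHWBPAS".

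The protocol does not say which kind of exercise referral scheme (ERS) result is the benchmark, and it states no limit on a causal reading of the change.

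**The concern.** Impact means the difference between what happened and what would have happened without the service. A before-after change in users alone does not identify that difference, however carefully it is analysed. The problem lies in the design and the stated inference, so it does not depend on model detail that a statistical analysis plan might add.

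The planned strata add two further problems. Grouping people by a baseline reading and then reporting change in that same reading makes the worst group look better at 12 weeks through measurement fluctuation alone. Grouping by adherence conditions on behaviour after baseline: people who keep attending may differ in health, motivation and circumstances, and their change may differ for those reasons.

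The results have downstream uses. Section 4.4 promises recommendations and best-practice guidance for other councils. Section 8 (work package 4) allows costs to be combined with outcome data such as change in blood pressure. A table that seems to show the service working best for the least healthy would bear directly on the protocol's theme of inequality.

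**Working it through.** The protocol gives no figure for this analysis (no sample size, SD or test-retest correlation), so there is nothing to reproduce. The check has four parts.

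**1. Design against inference.** Section 6 restricts the data to enrolled, consenting users. Section 8 compares each user's baseline with 12 weeks. Section 5 asks whether there is impact in line with other schemes. The observed mean change is the sum of the service effect, seasonal and secular change, the effect of other care, selection into 12-week measurement, and regression to the mean where entry followed an extreme reading. One before-after mean cannot separate these terms. A controlled ERS study reports a difference between groups, in which the shared terms cancel, so the two quantities are not comparable.

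**2. Regression to the mean within baseline strata.** Assume zero true effect, bivariate normal values with equal SD at both times, and correlation r between baseline and follow-up of the same index. The mean standardised baseline in the worst third is φ(0.431)/(1/3) = 1.091. The expected spurious improvement is 1.091 × (1 − r) SD. The values of r and of the systolic blood pressure SD below are assumptions.

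| r | Shift (SD) | If SD = 12 mmHg | If SD = 18 mmHg |
|---|---|---|---|
| 0.9 | 0.11 | 1.3 | 2.0 |
| 0.8 | 0.22 | 2.6 | 3.9 |
| 0.7 | 0.33 | 3.9 | 5.9 |
| 0.6 | 0.44 | 5.2 | 7.9 |

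The best third shows an equal apparent worsening.

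A simulation (2,000 runs per setting, paired t-test at two-sided 5%, zero true effect) shows how often this would look like a finding. The test and the total sample sizes are also assumptions.

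- r = 0.7: significant improvement in the worst third in 46%, 86% and 99% of runs at total N = 60, 150 and 300.
- r = 0.9: 18%, 42% and 69% of runs at the same sizes.
- All participants together, not selected on baseline: about 4% to 6% of runs, the nominal rate.

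**3. When the artefact shrinks.** For a stratifier correlated a with the baseline index and b with the 12-week index, the same argument gives 1.091 × (a − b) SD. The same-index case is a = 1, b = r. If the stratifier reflects only a stable level, such as a long-standing diagnosis, a = b and the artefact is zero. With assumed a = 0.40 and b = 0.36 it is 1.091 × 0.04 = 0.04 SD. The protocol does not define health status, and activity level is not among its example indices, so the text does not settle which case applies.

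**4. Follow-up.** Section 6 says: "The literature indicates that attrition for ERS may be up to fifty percent". The figure is used there to plan the interview sample. If it carried over to 12-week readings (an assumption), the mean change in all enrolled users would be 0.5 × (change in those measured) + 0.5 × (change in those not measured). If those not measured had not changed at all, the reported change would be twice the change in all enrolled users.

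**The case against.** Several objections have force.

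- **The data are supplementary and the text says whether.** Section 7 presents the quantitative data as a supplement to the interviews, and section 5 does not assert that the service works. Both points are right. The interviews also address perceived impact, so this is not the only outcome evidence in the work package. Even so, the analysis cannot answer the question of whether there is impact.
- **Selection on poor health is not shown.** A reader might infer that people enter because of a bad reading, so that regression to the mean inflates the overall change. The documents do not support this. Section 1.2 opens the service to nearly everyone, accepts self-referral, and sets no threshold on blood pressure, body mass index or wellbeing. The overall mean is affected only to the extent that entry followed extreme readings.
- **The strata may not be same-index.** Section 6 lists health status beside ethnicity and age, so it may be a category such as a diagnosis. The figures in the table are therefore conditional on how the strata are cut.
- **The benchmark may be within-group change.** Section 5 does not say that the comparison is with controlled studies. A comparison with before-after change in other schemes would be like with like as a measure, although differences in case mix and follow-up would remain and it would still not show impact.
- **Separate tests within strata are not stated.** A reader might infer a plan to compare groups by which stratum reaches significance. The protocol says only that results will be stratified, so no fault is claimed there.

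What stands is the mismatch between the stated inference and the design, and the confounding of change by adherence.

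**Conclusion.** Wrong as written, of moderate severity: section 5 states an inference that the design in sections 6 and 8 cannot deliver. This needs no numerical assumption.

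The size of the regression artefact is conditional. If strata are cut on the same index, the worst third appears to improve by 0.11 to 0.44 SD with no service effect, for assumed r from 0.9 to 0.6. The direction is certain for any r below 1. If the strata rest on a diagnosis, or activity level stratifies a different index, the artefact is smaller or absent. The blood pressure figures also rest on an assumed SD and are not predictions for this service.

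A reader might go further and infer that the evaluation will falsely show the service to work overall. The documents do not establish that. They establish only that an overall change could not be attributed to the service.

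**What to change.** 1. **Section 5.** State that the analysis describes 12-week change in service users, compared only with within-group change reported for users of other schemes, and is not interpreted as an effect of the service. Carry the same limit into any use of these changes in work package 4.
2. **Section 8, baseline strata.** Define health status. Do not stratify change in an index by the baseline value of that same index. If that relation is wanted, show the expected regression to the mean beside it, or use Oldham's method (change against the mean of the two readings).
3. **Section 8, adherence and follow-up.** Label the adherence strata as descriptive only, and report how many enrolled users have a 12-week value.

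A baseline-adjusted model comparing deprivation, ethnicity or age groups is not recommended as a remedy. These groups are not randomised. If their baseline means differ by d SD and nobody changes, adjusting for baseline gives a spurious difference of d × (1 − r), which is 0.5 × 0.3 = 0.15 SD at assumed d = 0.5 and r = 0.7.

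The cost is protocol wording and a small amount of extra reporting, with no new data collection. The downside is that the stated claim becomes less favourable.
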